3.0 STUDY OVERVIEW

The ULTRA study is a single-arm trial of 100 premenopausal women with symptomatic uterine fibroids who undergo treatment with the Radiofrequency ablation device. We will evaluate changes in fibroid-related symptoms from pre-treatment values to 3, 6, 12, 18, 24, 30, and 36 months after Radiofrequency ablation. We will also assess operative outcomes including procedure duration, complications, blood loss, post-operative pain, and return to usual activities. We will determine long-term efficacy of Radiofrequency ablation by evaluating the rate of re-treatment for symptomatic fibroids after the Radiofrequency ablation procedure.

Study participants will be recruited at 5 sites within the UC Fibroid Network: UC Davis, UC Irvine, UC Los Angeles, UC San Diego, and UC San Francisco. UC San Francisco will serve as the Coordinating Center for the trial with oversight of all scientific and administrative aspects of the study. All study data will be stored securely in a HIPAA compliant, secure database monitored by the UC San Francisco Coordinating Center. A data safety and monitoring board will oversee participant safety and protection.

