6.0 STUDY POPULATION

We will recruit women with symptomatic fibroids who meet the following criteria:

INCLUSION CRITERIA

1. Premenopausal (at least 1 menstrual period in last 3 months)
2. Age >21years
3. Fibroids are associated with heavy bleeding, pelvic pressure or discomfort, urinary or bowel symptoms, or dyspareunia
4. Desires surgical management of fibroids
5. Uterus ≤16 weeks in size
6. All fibroids ≤ 10cm in maximum diameter by ultrasound or MRI assessment *within the last year*.
7. Total number of fibroids ≤6 by ultrasound or MRI assessment *within the last year*. (For this study "Fibroids" will be leiomyomas > 2cm)
8. Had a Pap smear within the last 3 years with appropriate follow-up and treatment for cellular abnormalities
9. Endometrial biopsy indicates no hyperplasia or cancer (biopsy only required if age >45 years and has anovulatory heavy bleeding)
10. Able to tolerate laparoscopic surgery
11. Able to give informed consent

EXCLUSION CRITERIA

1. Planned treatment for infertility
2. Pedunculated fibroid with thin stalk (total stalk length is <25% maximum diameter of fibroid)
3. Intracavitary (FIGO Type 0) fibroid
4. Symptomatic fibroids are *only* FIGO Type 1 (submucosal with ≥ 50% intracavitary)
5. Planned concomitant surgical procedure in addition to treatment of uterine fibroids
6. Use of Essure or any other metallic, implantable device within pelvis
7. Pregnancy
8. Pelvic infection with the last 3 months
9. History of pelvic malignancy and/or pelvic radiation
10. Known or high suspicion for dense pelvic adhesions
11. Fibroids treated by myomectomy, uterine artery embolism, radio-frequency ablation, MRI Guided focused ultrasound, or cryomyolysis within the last 3 months

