5. **Sexual Health Outcomes in Women Questionnaire (SHOW-Q):** This is a sexual functioning measure used to assess the impact of pelvic problems on various domains of sexual functioning for women's health studies.

8.1.B Perioperative Outcomes

Perioperative outcomes will be assessed during surgery, immediately after surgery in the recovery room, and postoperatively for 6 weeks. We will collect standard perioperative variables for a surgical procedure to evaluate safety and efficacy including the duration of surgery, recovery time, and adverse events. Table 1 outlines key perioperative outcomes. Adverse events are described in section 9.0.

Table 1. Perioperative Outcomes	
Intraoperative Outcomes	
 • Procedure time 
 *skin to skin time *total OR time • Fibroids detected by intraoperative ultrasound, not visualized on preoperative imaging 
 *Total number *Location of each fibroid *3 dimensions in cm of each fibroid • Estimated blood loss • Unanticipated operative findings • Adverse events • Mechanical malfunction with equipment
Immediate Postoperative Outcomes (Recovery Room)	
 • Unplanned/unanticipated intraoperative procedures • Time in recovery room • Hospital admission • Gynecologist rating of procedure difficulty • Participant rating of pain on Visual Analogue Scale • Adverse events
Delayed Postoperative Outcomes (Within 6 weeks of Radiofrequency ablation)	
 • Days to return to normal activities • Days to return to work if applicable • Clinic or hospital visits related to surgery of fibroid symptoms • Adverse events • Pregnancies and pregnancy outcomes

8.1.C Long Term Operative Outcomes

Long term outcomes related to surgery will include measures related to treatment failure, long-term morbidity, and pregnancy as follows:

1. Treatment Failure: We will ask participants to report any additional fibroid treatment including medical management for fibroid-related symptoms, myomectomy, hysterectomy, uterine artery embolization, MR Guided Focused Ultrasound, endometrial ablation, dilation and curettage, or any new and emerging fibroid treatments.
2. Adverse Events

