12.0 STATISTICAL CONSIDERATIONS

The primary analyses will evaluate changes from baseline to 1, 3, 6, 12, 18, 24, 30, and 36 months after Radiofrequency ablation treatment in all patient-reported outcomes including scores for the UFS-QOL and other standardized symptom and quality of life questionnaires. We will use ANOVA to evaluate the overall differences among these multiple time points in change scores, adjusting for potential confounding factors and baseline values to increase power. We will test the normality assumption and use nonparametric alternative models if the normality assumption is violated. We will use paired t-tests to directly compare mean scores from baseline to all follow-up time points.

Additional Planned Analyses: Descriptive analysis of the following outcomes will be reported with proportions and standard deviations for categorical outcomes and means with standard deviations for continuous outcomes.

1. Operative Outcomes: We will report intraoperative and immediate and long-term postoperative outcomes as described in Section 8.1.B.
2. Treatment Failure: Treatment failure is defined as any additional treatment for fibroids after the Radiofrequency ablation procedure including medical management for fibroid-related symptoms, myomectomy, hysterectomy, uterine artery embolization, MR Guided Focused Ultrasound, endometrial ablation, dilation and curettage, or any new and emerging fibroid treatments.

3. Resource Utilization: Medical resource utilization is measured by the number of hospitalizations, unplanned physician or clinic visits, and missed days of work or usual activities due to Radiofrequency ablation treatment.
4. Pregnancy Outcomes: We will report the proportion of women who become pregnant following Radiofrequency ablation treatment among all study participants and among the subgroup of women who report that they are actively trying to become pregnant prior to undergoing Radiofrequency ablation. For women who do become pregnant during the study, we will report the proportion who undergo miscarriage, abortion, or live births. We will also report obstetrical and perinatal complications.

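### Natural menopause during the 36-month follow-up is neither a listed outcome nor handled in the analysis, so at 18–36 months it cannot be separated from lasting ablation benefit

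*Combined protocol and SAP*

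**What the plan says.** **Entry.** Section 6.0 defines the menopausal criterion as "Premenopausal (at least 1 menstrual period in last 3 months". Age has a lower bound only, and neither criteria list sets an upper one. Inclusion criterion 9 adds that endometrial "biopsy only required if age >45 years and has anovulatory heavy bleeding", so the protocol itself expects some women late in reproductive life with irregular cycles.

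**Design.** Section 3.0: "The ULTRA study is a single-arm trial of 100 premenopausal women with symptomatic uterine fibroids". It plans to evaluate "changes in fibroid-related symptoms from pre-treatment values to 3, 6, 12, 18, 24, 30, and 36 months after Radiofrequency ablation", and states: "We will determine long-term efficacy of Radiofrequency ablation by evaluating the rate of re-treatment for symptomatic fibroids".

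**Follow-up measures.** Section 8.1.C: "Long term outcomes related to surgery will include measures related to treatment failure, long-term morbidity, and pregnancy as follows". The items listed are treatment failure, adverse events and pregnancy. Table 2 in Section 8.1.D has rows for symptom questionnaires, perioperative outcomes and long-term operative outcomes. Neither place names menopausal status or last period.

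**Analysis.** Section 12.0: "The primary analyses will evaluate changes from baseline to 1, 3, 6, 12, 18, 24, 30, and 36 months after Radiofrequency ablation treatment", by ANOVA on change scores and by paired t-tests. On re-treatment: "Treatment failure is defined as any additional treatment for fibroids after the Radiofrequency ablation procedure". It is reported as a proportion. Pregnancies are described, but nothing is said about symptom scores completed during one. Menopause is not mentioned in Section 12.0.

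**The concern.** Some women who enter in the menopausal transition will stop menstruating before month 36. Their heavy bleeding then ends for a reason unrelated to the procedure, and with it much of their reason to seek further treatment for bleeding. Section 12.0 counts them as improved and free of treatment failure in the same way as a woman whose ablation has lasted.

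The study has no control arm to show the natural course. The evidence cited in Section 1.0 reaches 12 months, so months 18–36 are largely what this study adds, and that is where menopause accumulates. Waning of the ablation effect could be partly hidden there. Bleeding scores completed during pregnancy raise the same problem on a smaller scale, because women who desire future fertility are deliberately included.

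**Working it through.** **1. The plan's own yardstick.** Inputs from Section 12.0: N = 100, SD 21.7, 5% type 1 error, 90% power, detectable change 7.2. Treating 21.7 as the SD of the change and the test as two-sided (both assumptions):

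21.7 × (1.960 + 1.282) / √100 = 7.03 points (7.10 with the t distribution).

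Power at 7.2 points is 91.3% (normal) or 90.8% (t). The stated 7.2 reproduces. It is a power figure, not an expected effect.

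**2. Shift in the 36-month mean.** Shift = p × d, where p is the share of women reaching natural menopause by month 36 and d is the extra improvement menopause gives them beyond what ablation left. The documents give neither an age distribution nor a menopause rate, so both are assumed.

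| p | d = 5 | d = 15 | d = 25 |
|---|---|---|---|
| 5% | 0.25 | 0.75 | 1.25 |
| 15% | 0.75 | 2.25 | 3.75 |
| 25% | 1.25 | 3.75 | 6.25 |

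The range is about 0.3–6 points.

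**3. How large d can be.** Section 1.0 cites a 56% fall in symptoms at 12 months, which leaves 44% of baseline. If that effect persisted, a further 25-point fall would need a mean baseline of at least 25 / 0.44 = 57 points, even if menopause took the score to zero. Section 2.0 says this study enrols women with more moderate symptoms. The right-hand column is therefore plausible mainly where the ablation effect has waned.

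**4. Effect on a test at a late visit.** Suppose no ablation effect remained at all. With N = 100 and SD 21.7, a paired t-test would still be significant with probability 15%, 45% or 78% for menopause-driven shifts of 2.0, 4.0 or 6.0 points.

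**5. Re-treatment.** Assume a 36-month risk of 20% without menopause (not in the documents).

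- No risk in women who reach menopause: observed risk = 0.20 × (1 − p), or 19% at p = 5% and 15% at p = 25%.
- Half the risk removed: observed risk = 0.20 × (1 − p/2), or 19.5% and 17.5%.

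**6. Timing.** Few women can pass through menopause within 3–6 months of surgery, so p and the shift are near zero there. The 52% fall by 3 months cited in Section 1.0 could not be explained this way to any large extent.

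**The case against.** **The direction is not uniform.** A reader might infer that the bias always favours the device. The documents do not support that. Criterion 9 concerns anovulatory bleeding; if it persists or worsens before periods stop, scores worsen, and medication given for it as a fibroid symptom counts as treatment failure. Criterion 3 also admits women whose complaints are pressure, urinary, bowel or sexual, and the outcomes include the SF-36 and SHOW-Q. Nothing in the documents says these improve when bleeding stops. This objection stands: a likely direction can be stated only for bleeding-related scores and re-treatment.

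**The size is assumed.** This stands, as steps 2 and 3 show.

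**Age is a baseline covariate (Section 8.2, Table 3).** This helps little. Baseline age does not show who became menopausal, and in one arm adjustment for it cannot separate menopause from ablation effect.

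**The forms may already ask.** Questionnaire items and case report forms are not reproduced in the documents, so one cannot conclude that the information goes uncollected. Section 12.0 would still lack a rule for using it.

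**Planning of the randomized trial would not necessarily suffer.** With similar eligibility, menopause would occur in both arms, and all-participant means, SDs and re-treatment rates would be suitable planning inputs. This stands, and it confines the concern to how durability is interpreted.

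**This is a declared uncontrolled pilot.** True, and an all-participant result is a legitimate target. But Section 3.0 says re-treatment will determine long-term efficacy, and Section 12.0 claims power to evaluate efficacy.

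**Conclusion.** The point holds in limited form. Women in the menopausal transition can enrol and are followed for 36 months without a control. Neither the listed outcomes nor the analysis plan allows natural menopause to be separated from durable benefit at 18–36 months. For bleeding scores and re-treatment the likely net direction favours the device; for other outcomes no direction can be claimed.

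The size cannot be computed from the documents. The 0.3–6 point range rests entirely on assumed shares and gains; its low end is negligible and its high end requires loss of ablation effect. A reader might go further and infer that the late results would be invalid, or that the overall benefit could be explained by menopause. The documents do not support either inference, and early results are essentially unaffected. This is a cheap improvement to a pilot, not a flaw that undermines it.

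**What to change.** **Data.** Add to each follow-up questionnaire from month 3 the date of the last menstrual period and, if periods have stopped, the cause: natural menopause, pregnancy, medical treatment, or hysterectomy or other procedure. State in advance how long without a period counts as natural menopause.

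**Symptom scores (Section 12.0).** Keep the all-participant analysis as primary. Add a sensitivity analysis at 18–36 months that sets aside bleeding-related scores only after natural menopause or during pregnancy. Keep women whose periods stopped through hysterectomy or medical treatment for fibroids, and count them as treatment failures. A simple subset of women still menstruating should not be used: it would drop exactly those failures and flatter the device.

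**Re-treatment.** Report cumulative incidence with natural menopause as a competing event, or censor at menopause as a sensitivity analysis. The first shows how many women reached menopause before any re-treatment. The second estimates the risk had menopause not intervened, assuming censoring is uninformative.

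**Cost.** One item on questionnaires already sent by mail, online or asked by phone, and a smaller number in the sensitivity analysis. If 5–25 of 100 women were set aside, the detectable change by the formula in step 1 would rise from 7.03 to 70.34 / √95 = 7.22 or 70.34 / √75 = 8.12 points, before dropout. Eligibility does not change.

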6.1 Participant Recruitment

Study participants will be recruited through the clinical practices of ULTRA investigators and among the general community of women seeking fibroid treatment. Advertisements for the study will be posted on the fibroid centers' and/or department website and in key clinical areas within our women's health clinics. We will also post advertisements in local newspapers and community boards. Study investigators will identify patients with symptomatic fibroids who meet the inclusion and exclusion criteria and invite them to participate in ULTRA. Study investigators will explain the Radiofrequency ablation procedure as well as the study protocol. Potential study participants will be offered alternatives to Radiofrequency ablation treatment as clinically indicated and available including medical management for heavy bleeding, myomectomy, hysterectomy, uterine artery embolization, and MR Guided Focused Ultrasound.

[figure not shown]

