6.2 Informed Consent

The study aims and procedures will be explained initially by the study investigators during a fibroid consultation visit. A trained research coordinator will then confirm that the patient meets the inclusion and exclusion criteria and review in detail the study consent form and protocol with emphasis on the length of follow-up and required follow-up procedures. The study investigator will answer any additional questions about Radiofrequency ablation or study procedures. The study investigator will discuss with the participant the risk that the Radiofrequency ablation procedure cannot be performed at the time of surgery (e.g. due to dense pelvic adhesions) and inquire what alternative treatment options the participant would desire (e.g. an open abdominal myomectomy). The participant will then sign the study consent form. In addition, the participant will sign a standard surgical consent form unique to each study site that details the Radiofrequency ablation procedure, risks, benefits, and alternative therapies.

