7.2 The Radiofrequency ablation Procedure

The Radiofrequency ablation procedure will vary somewhat among study participants based on the size, number, and location of fibroids as well as the surgical protocols and practices at each study site. Gynecologists may select which laparoscopic port system is used and which laparoscopic entry procedure they prefer for the Radiofrequency ablation procedure. Any standard laparoscopic 10-12mm ultrasound probe may be used. However, all Radiofrequency ablation procedures will proceed with several uniform steps as follows:

1. Sequential compression devices are placed on the bilateral lower extremities.
2. Antibiotics are not given as surgical prophylaxis per ACOG guidelines for laparoscopy.
3. General anesthesia is induced.
4. A Foley catheter is placed in the bladder.
5. A pelvic exam is performed with note of the uterine size.
6. An IUD is removed if present.
7. A HUMI plastic uterine manipulator is placed in the uterus with the patient in dorsal lithotomy position (optional).
8. Grounding pads are placed on the bilateral thighs 1cm above the patella with good skin contact.
9. A 5mm umbilical port site is placed for a 5mm laparoscope.
10. A 10-12mm midline port site is placed for the ultrasound.
11. The ultrasound is used to locate and measure all uterine fibroids and fibroid measurements are recorded.
12. The Radiofrequency Probe is placed into the abdomen percutaneously under direct visualization.
13. The Radiofrequency Probe is used to perform the fibroid ablation following the Instructions for Use of the Radiofrequency ablation system. The ablation algorithm will guide the length of the ablation procedure. Care will be taken to avoid the pelvic sidewall, bladder, and bowel.

14. All fibroids visualized with intraoperative ultrasound are treated with the Radiofrequency Probe.
15. Submucosal fibroids are treated after removing the HUMI uterine manipulator. The HUMI uterine manipulator can be used to help position the Radiofrequency Probe in the fibroid, but then the manipulator is removed before heat is delivered to the fibroid.
16. The Radiofrequency Probe and laparoscopic ports are removed.
17. The 10-12 mm port site fascia may be closed at the discretion of the surgeon.
18. The skin is closed with surgical glue or sutures at the discretion of the surgeon.
19. The patient is discharged from the recovery room after meeting recovery room discharge criteria.

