7.3 Unanticipated Surgical Findings

At the time of surgery, unanticipated surgical findings may create an obstacle to performing the Radiofrequency ablation procedure (e.g. dense pelvic adhesions). In this case, the surgeon may elect to perform another fibroid treatment such as abdominal myomectomy or hysterectomy guided by the preoperative discussion with the participant regarding her desire under these circumstances. In addition, if an adnexal mass is visualized intraoperatively and the surgeon feels it should be removed, she/he may complete this surgery. Finally, if a subserosal or pedunculated fibroid is visualized that was felt to have a broad base but appears to have a narrow stalk, it may be removed via laparoscopic myomectomy.

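### Exclusion 2 is meant to keep out thin-stalked pedunculated fibroids, but its only numeric test is on stalk length, so applied literally it does not exclude a long thin stalk

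*Combined protocol and SAP*

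**What the plan says.** Section 6.0, exclusion 2, removes this type of fibroid: "Pedunculated fibroid with thin stalk (total stalk length is <25% maximum diameter of fibroid". The sections available for review do not define total stalk length, and they set no limit on stalk width, stalk thickness or base diameter.

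Two inclusion criteria in Section 6.0 bound the fibroid diameter to which the 25% applies. Every fibroid must be no more than "10cm in maximum diameter by ultrasound or MRI assessment", and fibroids for this study "will be leiomyomas > 2cm".

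Section 7.3 describes a related finding at operation, where "a subserosal or pedunculated fibroid is visualized that was felt to have a broad base but appears to have a narrow stalk". In that case "it may be removed via laparoscopic myomectomy". Otherwise step 14 of Section 7.2 applies: "All fibroids visualized with intraoperative ultrasound are treated with the Radiofrequency Probe".

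The criteria are applied twice. Under Section 6.1, "Study investigators will identify patients with symptomatic fibroids who meet the inclusion and exclusion criteria"; under Section 6.2, "A trained research coordinator will then confirm that the patient meets the inclusion and exclusion criteria".

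**The concern.** The words of exclusion 2 name one dimension and its number tests another. *Thin* describes width, as does the contrast in Section 7.3. The bracketed test uses length, and it excludes when the length is small. Lengthening a thin stalk therefore moves the woman towards eligibility, although the fibroid is still of the type the line names.

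What is at stake is consistent screening. Investigators and coordinators at five sites (Section 3.0) depend on this line, and someone checking a numeric rule may reasonably apply the number as written. The data and safety monitoring board reviews compliance with enrolment criteria (Section 10.0), which is hard to judge when the dimension to be measured is unclear. The first primary goal in Section 4.0 is to produce a template for later comparative trials, so the wording could be carried forward.

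**Working it through.** The 25% figure is a definition, so there is no derived figure to reproduce. The check applies the rule as written and asks where it parts from a width rule.

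**Inputs from the plan (Section 6.0).** Threshold 25% of maximum diameter D; D above 2 cm and at most 10 cm.

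**Assumed inputs.** Stalk length L and width W. The documents give no stalk dimensions, so all values below are illustrative.

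**Step 1: the cut-off.** Cut-off = 0.25 × D.

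- D just above 2 cm: just above 0.5 cm
- D = 8 cm: 0.25 × 8 = 2.0 cm
- D = 10 cm: 0.25 × 10 = 2.5 cm

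**Step 2: two tests on an 8 cm fibroid (cut-off 2.0 cm).**

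| Stalk, length × width (cm) | Length test as written (L < 2.0) | Width test (W < 2.0) |
|---|---|---|
| 3 × 1 | not met | met |
| 1 × 1 | met | met |
| 1 × 3 | met | not met |
| 3 × 3 | not met | not met |

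The tests disagree for a long thin stalk and for a short broad one.

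**Step 3: where a long thin stalk passes the length test but fails the width test.** This needs W < 0.25 × D ≤ L, that is, 4W < D ≤ 4L. It can happen only if the stalk is longer than it is wide. With W = 1 cm:

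- L = 3 cm: 4 < D ≤ 12, so every fibroid above 4 cm up to the 10 cm cap
- L = 1.5 cm: 4 < D ≤ 6
- L = 1 cm: 4 < D ≤ 4, so never

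These ranges show where the two tests differ. They do not prove that 25% of diameter is the right limit for width, because the plan never states a width limit.

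**Step 4: ways to read the line.**

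- The bracket is the whole definition of thin. The 3 × 1 stalk is let in, and the 1 × 3 stalk is kept out.
- Thinness and the bracket must both hold. The 3 × 1 stalk is still let in. The 1 × 3 stalk is not thin, so it is correctly not excluded.
- Length means the extent of the attachment. Both stalks are handled as intended, but the wording does not say this.

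The long thin stalk gets through unless the third reading is adopted. The short broad stalk is a problem under the first reading only.

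**The case against.** The best reply is that the intent can be recovered. The line opens with the word thin, Section 7.3 speaks of base and narrowness, and a gynaecologist reading both would probably take length to mean the extent of the attachment. That is fair, and it is the main reason the point is minor. It is not a reason to leave the line, because the number still sits on the wrong dimension.

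Other limits also stand. Exclusion 3 removes intracavitary fibroids whatever their stalk, so the gap mainly concerns subserosal pedunculated ones. Screening involves clinicians as well as a coordinator. The three readings are not equally likely, so counting how many of them fail carries no weight.

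Two replies carry less. Section 7.3 does offer a remedy in theatre, but it is permissive and covers only a fibroid first thought to have a broad base. It does not cover one recognised beforehand as thin-stalked and passed on length. The forms and manual of operations mentioned in Section 2.0 might say how to measure a stalk, but they were not available and cannot be assumed to correct the protocol.

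A reader might go further and infer that ineligible women were enrolled or harmed, or that the symptom results are distorted. The documents support neither. They give no stalk measurements, no count of pedunculated fibroids, and no report of misclassification.

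**Conclusion.** The concern holds as a minor wording error in an eligibility rule. Exclusion 2 aims at a width feature and tests length, so applied literally it does not exclude a long thin stalk. The plan's own figures fix only the range of the cut-off, from just above 0.5 cm to 2.5 cm; the worked stalks rest on assumed dimensions. How many women the wording could affect is unknown.

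The conclusion assumes that the target is stalk width, which the word thin and Section 7.3 both support. It does not assume that 25% is the right width limit. A reader might also infer that the rule wrongly excludes every short broad stalk. That follows only if the bracket is read as the full definition and the word thin is given no separate force. Sample size, power and the planned analyses do not depend on this line.

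**What to change.** In exclusion 2, replace *total stalk length* with *stalk width (diameter at its narrowest point)*, and keep the comparison as below 25% of maximum fibroid diameter. The sponsor's clinicians should confirm two things first:

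- **Measurement site.** Narrowest point and attachment to the uterus give different answers for a stalk that flares at its base. A measurement at the attachment could let through a stalk that is thin in the middle.
- **Cut-off.** They should confirm that 25% was meant for width.

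Recording stalk width at screening for pedunculated fibroids would help but is optional. The cost is one term in one line plus that clinical confirmation, with no change to sample size, visit schedule or analysis.
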